The primary purpose of the current proposal is to obtain preliminary data to increase the likelihood of funding for a future NIH grant, while balancing the feasibility of completing the current proposal. To that end, we will utilize a within-subject, repeated measures design to assess the feasibility of administering pioglitazone for four weeks to non-treatment and treatment-seeking individuals with AUD and elevated levels of stress/anxiety (**N=20**). Participants will undergo pre- and post-treatment human laboratory assessment of stress-reactivity and stress-induced alcohol craving. During treatment, changes in alcohol use, stress/anxiety, and alcohol craving will be assessed in the natural environment. The study design features 1) rigorous monitoring of medication compliance (Medication Event Monitoring System (MEMs)) and alcohol use (urinary ethyl glucuronide (ETG)); 2) biological assessment of stress reactivity (salivary cortisol, blood pressure, and heart rate); and 3) a multi-dimensional assessment of stress-induced alcohol craving incorporating both traditional measures of alcohol craving in addition to relatively novel behavioral economic measures (delay discounting, alcohol demand). Taking these measures together, we hope to present a robust and comprehensive characterization of pioglitazone on alcohol use, stress reactivity, and stress-induced alcohol craving.

SPECIFIC AIMS

Specific Aim 1: To assess pre- to post-treatment reductions in stress reactivity (self-report, salivary cortisol, heart rate, blood pressure) and stress-induced alcohol craving (self-report, alcohol demand) in the human laboratory setting.

Hypothesis 1: *We will observe pre- to post- treatment reductions in stress reactivity and stress-induced alcohol craving.*

Specific Aim 2: To assess changes in alcohol drinking (drinks per day, heavy drinking days), stress/anxiety (PSS, HAMA, PCL-5), and alcohol craving (PACS, delay discounting, alcohol demand) during treatment in the natural environmental setting.

Hypothesis 2: *We will observe decreased alcohol drinking, stress/anxiety, and alcohol craving over the course of treatment.*

There is increasing attention and evidence supporting the potential role of the PPAR γ system as a novel target in the treatment of AUD. From a translational perspective, this study is timely and likely to advance our understanding of stress as a mechanism of action of pioglitazone effects.

IRB NUMBER: HSC-MS-18-0922

BACKGROUND AND RATIONALE

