and predict alcohol treatment response³⁹⁻⁴². Delay discounting and alcohol demand are poorly correlated with each other, supporting a multi-dimensional model in which these measures represent distinct aspects of motivation to use alcohol⁴²⁻⁴⁸. In the current proposal, we will assess changes in both delay discounting and alcohol demand over Study Weeks 0 to 4 and alcohol demand will be used to assess state-dependent changes during the human laboratory stress-reactivity assessment.

METHODS

Research team. The research team will consist of [name] (PI) and a number of collaborators from UTHealth and Brown University. [name] (PI) is an experienced addiction researcher and an expert in assessing behavioral economic measures in addiction research, which is pertinent to the current project. Drs. [name] (CNRA Medical Director) and [name] (Addictions Psychiatrist) will provide medical guidance and ensure participant safety over the course of the study. [name] is Professor and Vice Chair for Research and directs the Behavioral Laboratory at the CNRA with expertise in medication development trials as well as alcohol studies. [name] is a biostatistician and data scientist with expertise in experimental design and statistical modeling, including the type of generalized linear modeling that will be utilized by the present research. From Brown University, [name] (Co-I) is serving as a consultant on this project and is an expert in stress and alcohol research¹⁻⁷. Additionally, our group has a history of collaborating with the Laboratory of Biomarkers located in the BBSB for analyzing biological samples, such as salivary cortisol in the current protocol. We will work with [name] to ensure that samples are collected and analyzed appropriately.

Overall study design. We will utilize a within-subject, repeated measures design. Participants will receive pioglitazone or placebo for four weeks. A summary of the study timeline, procedures, and assessments is shown in the following Table.

Table 1. Outline of Study Timeline, Procedures, and Assessments

Study Week Procedures and Assessments	0	1	2	3	4
Consent and Baseline Screening SCID, ASI, KMSK, TLFB, CIWAA, AUDIT	X				
Receive Study Medication (Pioglitazone or Placebo) Assess Medication Compliance and Adverse Events	X	X	X	X	X
Human Laboratory Procedures (Specific Aim 1) Stress-Reactivity Assessment (Salivary Cortisol, HR, BP, Craving) Alcohol Demand, Alcohol Ladder	X				X

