Natural Environment Procedures (Specific Aim 2). At Study Week 0, all participants will receive a pamphlet copy of the “Rethinking Drinking: Alcohol and Your Health” providing research-based information related to alcohol use (RethinkingDrinking.niaaa.nih.gov). Research staff will go over the pamphlet’s information with the participant at the initial visit and subsequent visits as necessary. At each study visit, participants will receive study medication for the week and assessed for adverse events and medication compliance. At each visit, participants will also be assessed for recent alcohol use (self-report, ETG, BrAC), alcohol craving (PACS), and stress/anxiety (HAM-A, PSS). At the end of the study, participants will be referred to local alcohol treatment services as needed.

Participant Payment & Compensation. Participants will receive be able to receive \$300 for completing the study (\$50 for completing baseline screening; \$25 for each visit (\$100); \$25 for stress reactivity assessments (\$50); and \$100 completion bonus). Additionally, participants will potentially receive \$10/week (up to \$40) for demonstrating medication compliance. Participants will also receive parking/bus fare compensation at each visit worth \$5.

DATA ANALYSIS PLAN

General Data Analytic Strategy. Analyses will proceed in parallel using frequentist and Bayesian statistical inference. Frequentist analyses will examine relationships between predictors and outcomes using traditional measures of effect size and statistical significance (i.e., regression coefficients, standard errors,

confidence intervals, and p -values), while Bayesian analyses will measure uncertainty in model parameter estimates via posterior distributions and directly evaluate the probability of the alternative hypothesis.

Specific Aim 1: assess pre- to post-treatment reductions in stress reactivity (self-report, salivary cortisol, heart rate, blood pressure) and stress-induced alcohol craving (self-report, alcohol demand) in the human laboratory setting.

Hypothesis 1: We will observe pre- to post- treatment reductions in stress reactivity and stress-induced alcohol craving. Generalized linear mixed modeling will be used to evaluate each outcome as a function of time (pre-test and post-test) in unique models.

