Specific Aim 2: Demonstrate reduced alcohol drinking (drinks per day, heavy drinking days), stress/anxiety (PSS, HAMA, PCL-5), and alcohol craving (PACS, delay discounting, alcohol demand) during treatment in the natural environmental setting.

Hypothesis 2: We will observe decreased alcohol drinking, stress/anxiety, and alcohol craving over the course of treatment. Generalized linear mixed modeling will be used to evaluate each outcome as a function of time in unique models. Alcohol consumption will be modeled via drinks per drinking day, such that the number of positive drinking episodes a participant experienced in a week will be included as a count outcome (i.e., Poisson-distributed) and the number of drinking days in a week will be controlled for as an off-set covariate.

Power/Sample Size Considerations. The frequentist framework using null hypothesis statistical testing can provide some understanding of changes over time for each outcome. However, in evaluating a small within-subjects pilot trial of $N = 20$ participants, Bayesian statistical inference provides a superior framework for deriving evidence regarding the magnitude and direction of change over time for each model. The posterior probability of each effect would then be useful to inform effect sizes for power calculations and/or prior distributions in future research. As due diligence, however, a conventional frequentist power analysis follows. For the current proposal, power estimates are calculated using G*Power 3.1.9.2 and focus on reduction in alcohol consumption. Assuming alpha = 0.05 (one-tailed), an average baseline rate of 10.5 drinks/week across all participants (averaged between 14 and 7 drinks/week for male and female participants, respectively), a sample size of $N = 20$ participants provides 80% power to detect a 20% decrease in alcohol consumption over five weeks.

REFERENCES

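### The plan offers time-only, pre-to-post effects as inputs for future effect sizes and priors; that change is not a drug effect and could bias the next trial, probably toward undersizing

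*Combined protocol and SAP*

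**What the plan says.** The Abstract gives the aim of the pilot: "The primary purpose of the current proposal is to obtain preliminary data to increase the likelihood of funding for a future NIH grant". It also names feasibility of four weeks' dosing.

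The General Data Analytic Strategy says that "Bayesian analyses will measure uncertainty in model parameter estimates via posterior distributions and directly evaluate the probability of the alternative hypothesis". The Power/Sample Size section adds that "Bayesian statistical inference provides a superior framework for deriving evidence regarding the magnitude and direction of change over time for each model", and then links the results to later work: "The posterior probability of each effect would then be useful to inform effect sizes for power calculations and/or prior distributions in future research".

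The models are specified by aim. For Aim 1: "Generalized linear mixed modeling will be used to evaluate each outcome as a function of time (pre-test and post-test) in unique models". For Aim 2: "Generalized linear mixed modeling will be used to evaluate each outcome as a function of time in unique models". Neither has a treatment or treatment-by-time term.

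On design, the Overall study design section says "We will utilize a within-subject, repeated measures design" and, directly after, "Participants will receive pioglitazone or placebo for four weeks". Table 1 repeats the mention of placebo. No allocation method, ratio or sequence is given, and no analysis uses a placebo group.

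**The concern.** The sentence on future use is where the analysis plan connects this trial's results to its stated purpose. What it offers for reuse is change over time in people followed from week 0 to week 4. A later efficacy trial would need the difference between drug and control. The two are equal only if nothing but the drug moves the outcomes.

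The protocol itself names several other things that could move them:

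- Entry requires heavy drinking in the past month (Participants, Recruitment, and Setting). Selecting on a high value invites regression to the mean in drinking.
- Entry requires craving to rise at the baseline stress test (same section). This selects on the baseline value of an Aim 1 outcome.
- Everyone receives a drinking-advice pamphlet, which staff go through with them (Natural Environment Procedures).
- Assessment is repeated weekly, and the stress test is done twice (Table 1).

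Most of these push toward apparent improvement. The plan nowhere cautions that the change is not a drug effect. If the figure were reused as one, a later trial could be planned on too large a difference, or could start from a prior already favourable to the drug.

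A smaller fault is in the wording. A posterior probability, read literally, is not a quantity that can enter a power calculation.

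**Working it through.** **Inputs from the documents.** N = 20; alpha 0.05 one-tailed; baseline 10.5 drinks/week; a 20% decrease, which is 0.20 × 10.5 = 2.1 drinks/week; 80% power. The SD of change, within-person correlation, test, exposure, priors and allocation are not stated.

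**1. The plan's own 80%.** It cannot be reproduced from the stated inputs alone. One-sided variants give:

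- paired t-test with Poisson variance 10.5 and correlation 0, 0.25 or 0.5: 63%, 74% or 87%;
- Poisson regression with a binary predictor: 49% (20 observations, one week), 73% (40 observations) or 97% (20 observations, five weeks);
- paired Poisson rate ratio, week 0 against week 4: 70%.

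The point here does not depend on this figure. For illustration only, a one-sided paired t-test with n = 20 has 80% power at a standardised change of 0.577, so the implied SD of change is 2.1 / 0.577 = 3.64 drinks/week. That SD is back-solved, not stated.

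**2. What a posterior probability fixes.** With a flat prior and a normal approximation, a 0.95 probability of a decrease implies a mean decrease of 1.645 × SD / √20. For an assumed SD of change of 2, 3.64, 6 or 10 this is 0.7, 1.3, 2.2 or 3.7 drinks/week, or 7%, 13%, 21% or 35% of 10.5. The same probability fits all four.

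**3. Sizing a later trial on the full change.** Assume a two-arm, two-sided 5% trial sized for 80% power on the whole pre-to-post change, so that the expected Z is 1.96 + 0.84 = 2.80. Let f be the share of the change due to the drug. Then

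power = Φ(2.80f − 1.96) + Φ(−2.80f − 1.96), and the required sample is multiplied by 1/f².

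| f (assumed) | Power | Sample multiplier |
|---|---|---|
| 1.00 | 80% | 1 |
| 0.75 | 56% | 1.8 |
| 0.50 | 29% | 4 |
| 0.25 | 11% | 16 |

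Neither column depends on the SD. A prior for the drug effect centred on the full change would sit at 1/f times the true effect: 1.33, 2 or 4 times.

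**4. The same in participants.** With 1:1 allocation and SD 3.64, n per arm = 2 × (1.96 + 0.84)² × 3.64² / difference². For 2.1 drinks/week this gives 48 per arm. For 1.575, 1.05 and 0.525 (f = 0.75, 0.50, 0.25) it gives 84, 189 and 755. With 48 per arm, power is 56%, 29% and 10% (favourable tail only, hence 10% rather than 11%).

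**5. The other direction.** If untreated drinking would have risen by 25% of the observed change, the drug effect is 1.25 × 2.1 = 2.625. Then 31 per arm would do, and 48 gives 94% power: oversized.

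**6. If a placebo group exists and is pooled.** Assume 1:1 allocation, non-drug change c and drug effect δ. A time-only model estimates c + 0.5δ. This exceeds δ only if c > 0.5δ, but it equals δ only by coincidence.

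**The case against.** The strongest reply is that the sentence is a rationale, not a rule. It says the results would be useful to inform later work; it fixes no future design, comparator or sizing method. That stands. A reader might infer that the plan commits the next trial to this number; the text does not say so.

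A reader might also infer that the Bayesian output carries no magnitude at all. The documents do not support that. They plan posterior distributions of the model parameters, state magnitude and direction of change as the target, and run parallel frequentist analyses with coefficients and confidence intervals. In context, posterior probability is loose wording for the posterior of each effect, and naming the right summary cures it.

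A third inference, that the next trial is bound to be undersized, also goes too far. The drug shares are assumed, and step 5 shows the direction can reverse. What the documents do support is a likely direction, through the entry criteria and the pamphlet.

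Nor does the plan say that only positive-looking outcomes would be carried forward. It speaks of each effect and each model, so inflation from selecting on significance cannot be charged to it.

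Finally, the placebo wording means the design cannot simply be called uncontrolled. It is the specified analysis that is uncontrolled. None of these replies makes a time-only change into a drug effect, and the plan gives no warning that it is not one.

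**Conclusion.** The concern holds in a limited form. All planned models are time-only, so the effects offered for future effect sizes and priors are pre-to-post changes, not drug effects. Reuse as a drug effect could bias the next trial, probably toward undersizing: power of about 56%, 29% or 11% instead of 80% if the drug accounts for 75%, 50% or 25% of the change.

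Those figures rest on an assumed range of shares and an assumed two-arm, two-sided 5% trial sized on the full change. They do not depend on the SD. The likely direction rests on the entry criteria, the pamphlet and repeated assessment; it would reverse if untreated drinking would have risen. The posterior-probability wording is a minor fault. The conduct of the present trial is not affected; the stated use of its results is.

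**What to change.** Replace the sentence on future use with wording such as:

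> For each outcome we will report the posterior median and 95% credible interval of the pre-to-post change, labelled as such. This change is not an estimate of the drug-versus-control difference and will not be used as that effect size or as a prior for the drug effect. For planning, the pilot will supply the SD of change, within-person correlation, count dispersion, attrition and compliance.

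Reconcile the references to placebo in the Overall study design section and Table 1 with the time-only analysis. If there is a placebo group, describe the allocation, add treatment and treatment-by-time terms to the models, and carry forward the posterior of that contrast with its interval. If there is none, remove the references to placebo.

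The choice of prior for a later trial can be left to that trial's protocol, provided the pre-to-post posterior is not used for the drug effect.

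The cost is analysis-plan wording, plus model terms if a placebo group exists. The downside is that the grant application cannot quote the pre-to-post change as the expected drug effect.

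### The 80% power is set out in drinks per week, but the only alcohol model written out is a rate per drinking day, which excludes falls from fewer drinking days and is undefined in weeks without drinking

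*Combined protocol and SAP*

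**What the plan says.** All the relevant text is in the Data Analysis Plan.

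- **Power/Sample Size Considerations.** One-tailed alpha of 0.05, N = 20, and "an average baseline rate of 10.5 drinks/week across all participants (averaged between 14 and 7 drinks/week for male and female participants, respectively"). The conclusion is that these "participants provides 80% power to detect a 20% decrease in alcohol consumption over five weeks". The software is named (G*Power), but the test and the variance are not. The calculation is presented as due diligence beside a preferred Bayesian analysis.
- **Specific Aim 2, Hypothesis 2.** "Alcohol consumption will be modeled via drinks per drinking day". The response is specified so that "the number of positive drinking episodes a participant experienced in a week will be included as a count outcome", Poisson-distributed, and "the number of drinking days in a week will be controlled for as an off-set covariate".
- **Specific Aim 2, outcome list.** The aim is to "Demonstrate reduced alcohol drinking (drinks per day, heavy drinking days"). The general rule is "Generalized linear mixed modeling will be used to evaluate each outcome as a function of time in unique models". No distribution or offset is given for drinks per day or for heavy drinking days.

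**The concern.** One label, alcohol consumption, covers two quantities. The power statement gives only one rate, and it is in drinks per week. The analysis text gives only one fully specified alcohol model, and it is a rate per drinking day. Three things follow if that model is used as written.

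1. The count is of episodes. At one episode per drinking day the modelled ratio is 1 in every week, however much is drunk.
2. If the count is meant to be drinks, the offset fixes the coefficient of log(drinking days) at 1. The time effect then describes drinks per drinking day only, and a participant who cuts down by drinking on fewer days shows no change.
3. A week with no drinking days has offset log(0). No handling is stated. If such weeks are omitted, participants who stop drinking leave the model.

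The consequence goes beyond the frequentist power figure, because the outcome definition also governs the Bayesian model. The plan says "The posterior probability of each effect would then be useful to inform effect sizes for power calculations". An effect per drinking day, carried forward as an effect on total drinking, would mis-size the next study.

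**Working it through.** **Inputs from the power paragraph:** N = 20; 10.5 drinks/week, which is (14 + 7)/2; ratio 0.80, so 10.5 falls to 8.4; one-sided alpha 0.05 (z = 1.645). **Inputs assumed here:** five weekly counts (Weeks 0 to 4), a log-linear fall, Poisson variance.

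**Step 1: the plan's own figure.** Slope β = ln(0.80)/4 = −0.0558 per week. Weekly means μ = 10.5, 9.93, 9.39, 8.88, 8.40. The μ-weighted mean week is 1.889, and Σμ(t − 1.889)² = 93.83. Information I = 20 × 93.83 = 1876.5, so SE = 1/√1876.5 = 0.0231. Then |β|/SE = 2.417, and power = Φ(2.417 − 1.645) = 78%. Using the null variance for the critical value gives 80.6%. Other readings differ: one week before against one week after gives 69.5%, and Week 0 against Weeks 1–4 pooled gives 88.1%. A paired t-test gives 80% only if the SD of the change is 3.64 drinks/week, which is not stated. The 80% is therefore compatible with a weekly-drinks trend but cannot be tied to one test.

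**Step 2: the offset model, count read as drinks.** Weekly drinks = drinking days × drinks per drinking day. Let s be the share of the log fall that comes from fewer days; the documents do not give it. The offset model sees only (1 − s)β, so power = Φ((1 − s) × |β|/SE − 1.645).

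| Share s | Fall in drinks per drinking day | Power, 10.5/week | Power, 14/week | Power, 21/week |
|---|---|---|---|---|
| 0 | 20.0% | 78% | 87% | 96% |
| 1/4 | 15.4% | 57% | 67% | 82% |
| 1/2 | 10.6% | 33% | 40% | 53% |
| 3/4 | 5.4% | 15% | 17% | 21% |
| 1 | 0% | 5% | 5% | 5% |

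The columns for 14 and 21 are included because 10.5 is the midpoint of the entry cut-offs. If the weekly cut-offs apply to everyone and the sexes are balanced, the true mean is higher.

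A case at s = 1: 3.5 days × 3 drinks = 10.5 falls to 2.8 days × 3 drinks = 8.4. That is exactly the powered 20% fall, yet drinks per drinking day stays at 3.

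**Step 3: the same allowance for weekly drinks.** Without the offset, week-to-week variation in drinking days enters the residual variance. If days are binomial out of 7 (an assumption), the variance multiplier is φ = 1 + m(1 − d/7), where m is drinks per drinking day and d is mean drinking days. Power = Φ(|β|/(SE√φ) − 1.645). The offset model, with Poisson variance given days, has at least this power up to s = 1 − 1/√φ.

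| Baseline | φ | Power, weekly drinks | Offset model at least as powerful up to s = |
|---|---|---|---|
| 10.5/week over 3 days | 1 + 3.5 × 4/7 = 3.0 | 40% | 0.42 |
| 14/week over 4 days | 1 + 3.5 × 3/7 = 2.5 | 55% | 0.37 |
| 21/week over 5 days | 1 + 4.2 × 2/7 = 2.2 | about 75% | 0.33 |

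Which outcome has more power therefore depends on s and on how much drinking days vary. Neither is given.

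**The case against.** The strongest reply is that Aim 2 names drinks per day and heavy drinking days, and that each outcome is to have its own model. Drinks per calendar day is weekly drinks divided by 7, and heavy drinking days can also respond to frequency. An analysis sensitive to drinking days is therefore not excluded. This stands, and it makes the point conditional. It does not remove the point, because the sentence that specifies how alcohol consumption is modelled names a different quantity, and nothing says that a calendar-day model is kept beside it.

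Second, the word episodes is probably a slip, since the same sentence opens by naming drinks per drinking day. I agree. It needs a one-word correction, and the power figures above do not rely on the literal reading.

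Third, this is a pilot of 20 whose frequentist power is secondary. That lowers the weight, but the outcome definition carries into the Bayesian estimates as well.

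A reader might go further and infer that the 80% is miscalculated, that true power is 33% or 5%, or that weekly drinks would be the more powerful outcome. The documents support none of these. The test and variance are unstated, and a plausible trend test gives 78 to 80.6%. The 5% row needs the whole fall to come from fewer days, and at 21/week a quarter share still leaves 82%. Step 3 shows that the written model can have more power than weekly drinks.

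**Conclusion.** The point holds as a mismatch between the outcome behind the 80% and the only alcohol model written out, conditional on drinks per day not being modelled separately. The undefined offset in weeks without drinking is a gap in the written model whichever reading is taken.

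The size is a sensitivity, not a proven shortfall: at 10.5/week the offset model runs from 78% down to 5% as the share due to fewer days goes from none to all. This assumes Poisson variance, a log-linear fall over five weekly counts and no dropout. Weekly drinks are not safe at 80% either, with 40 to 75% under binomial drinking days in the cases shown.

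The main reason to change is therefore not a gain in power. It is that the alcohol result should answer the question about total drinking and keep abstinent weeks. This should be settled before analysis, so that the outcome is not chosen after the data are seen.

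**What to change.** Before analysis:

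- Make the main alcohol model the weekly count of drinks (equivalently drinks per calendar day, which Aim 2 already names), with no drinking-days offset, weeks without drinking kept as zeros, and allowance for over-dispersion.
- Keep drinks per drinking day as a secondary measure, defined among weeks with drinking.
- Replace episodes with drinks in the Hypothesis 2 text.
- Restate power or interval width for the main outcome, naming the test and variance, over a range of baselines and variances. For a Week 4/Week 0 ratio of 0.80 in weekly drinks, the 95% interval from the trend model is 0.67–0.96 at Poisson variance and 0.62–1.03 at twice that for 10.5/week. For 21/week it is 0.70–0.91 and 0.67–0.96.

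The cost is rewording and a short recalculation. Self-reported alcohol use is already collected at each visit (Natural Environment Procedures), so no new data are needed. The downside is that the restated power may be less favourable than 80%.

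The references to placebo in Overall study design and Table 1, against the single-group description in the Abstract, are a different issue and should be raised separately.
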